
Potential adverse events include heparin-associated risks, such as allergic reaction, major bleeding, minor bleeding, thrombocytopenia, and heparin induced thrombocytopenia (HIT), or any other adverse reaction suspected secondary to drug administration. All subjects enrolled in the study and received any UFH will be included in the safety evaluation.

A member of the research staff will collect the study data. All data required by the study protocol will be documented in the inpatient electronic medical record system. De-identified subject information will be written on Case Report Forms (CRFs) and all data collected will be stored in locked files at the Hemophilia Center of Western Pennsylvania (HCWP). Additionally, data will be entered into research electronic capture (REDCap) and compared to ensure consistency. No personal identifiers will be associated with the data. The Institutional Review Board (IRB) may inspect records at any time.

A sample size of 20 subjects for the pilot study is based on clinical rather than statistical considerations and should provide a preliminary estimate of primary and secondary clinical outcomes and assess prespecified feasibility criteria as detailed above. Based on 75,000 to 100,000 African Americans with SCD in the United States who develop ACS at a frequency of 8.8 per 100 patient years, with 50% developing ACS at some point during his or her lifetime, and given the fact that approximately 30 patients are admitted annually at UPMC hospitals (Presbyterian, Montefiore, Magee, Shadyside) with ACS, we estimate that at least 80%, or 24 patients per year, will meet inclusion and exclusion criteria, and expect to enroll 10 patients, or slightly less than 50% per year, which should meet the n=20 subjects required for the pilot study.^{3,4} This is a pilot feasibility study, so comparisons will be descriptive, including frequencies and percentages for categorical variables and mean, median, range, and standard deviation for continuous variables.

Demographics and medical information will be summarized with descriptive statistics as well. Adverse events will be summarized by frequency, relatedness, and severity.

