4.3 Inclusion/Exclusion Criteria

Inclusion criteria:

1. Diagnosis of ACS defined as a new pulmonary infiltrate involving at least one segment of the lung on a chest x-ray or chest CT scan with 2 or more of the following: chest pain, tachypnea (defined as a respiratory rate greater than 20 breaths per minute), dyspnea, cough, hypoxemia (see 3.3 Data Collection and Statistical Considerations for definition of hypoxemia), or body temperature greater than or equal to 38.0 degrees Celsius.

2. Hemoglobin electrophoresis confirming (HbSS, SC, or S β^0) (historical records sufficient).

3. Age greater than or equal to 18.

Exclusion Criteria:

1. Any absolute contraindication to heparin, including known bleeding diathesis, history of HIT, or history of an allergic reaction.

2. Platelet count less than 50 per microliter (current admission).

3. Historical diagnosis of moyamoya disease as documented in medical records.

4. Historical diagnosis of proliferative retinopathy as documented in medical records.

5. Current participation in a chronic exchange transfusion program.

6. Underlying hypercoagulable disorder other than SCD.

7. Currently receiving therapeutic anticoagulation.

8. Currently receiving antiplatelet agents.

9. Currently receiving estrogen containing oral contraceptives.

10. Chest CT scan documented PE performed as standard of care prior to study enrollment (current admission).

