Heparin therapy, like any other form of anticoagulation, increases the risk of bleeding. The risk of bleeding with UFH varies among clinical settings. The risk of bleeding with intravenous UFH in acute VTE is less than 3%.²⁰ Bleeding may be major, defined as a decrease in hemoglobin 2 grams per deciliter or more; transfusion of 2 or more units of red blood cells; or bleeding in a critical organ, such as intracranial, intraspinal, intraocular, pericardial, or retroperitoneal.²¹ The presence of major bleeding will result in the permanent discontinuation of UFH. If major bleeding occurs, protamine will be administered to reverse the anticoagulant effects of heparin. Protamine may result in hypotension, bradycardia, dyspnea, flushing, feeling of warmth, nausea, vomiting, or rarely anaphylaxis.¹⁴ Other medical interventions, such as intravenous fluids and red blood cell transfusions, will be administered as deemed appropriate. Minor bleeding is defined as all bleeding episodes that do not meet criteria for major bleeding. The treatment of minor bleeding may vary and will be determined by the specific clinical scenario. The decision to discontinue UFH in the setting of minor bleeding, permanently or only for a brief period of time, will be at the investigator's discretion. A known history of a bleeding diathesis will result in exclusion from study participation.

3. Thrombocytopenia

The risk of non-immune related thrombocytopenia with heparin varies anywhere between 5 and 30%.²² Thrombocytopenia will be defined as a platelet count less than 100,000 per microliter. UFH will be discontinued if the platelet count is less than 50,000 per microliter and may be resumed if the platelet count increases to greater than 50,000 per microliter during the study period. A baseline platelet count less than 50,000 per microliter will result in exclusion from study participation.

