4. HIT

HIT is an immunologically mediated thrombotic state that occurs in 1-2% of patients receiving heparin therapy.²³ Antibodies of the IgG class recognize large macromolecular complexes of platelet factor 4 bound to heparin.²³ Subsequently, these antibodies produce strong activation of platelets by binding to platelet Fc γ IIa receptors.²³ The ensuing thrombotic state may lead to arterial and venous thrombosis, skin necrosis, venous limb gangrene, stroke, and myocardial infarction. The diagnosis of HIT is a clinical-pathologic syndrome, which means the diagnosis requires a compatible clinical picture and laboratory evidence of platelet activating antibodies.²³ The laboratory diagnosis of HIT will be made with the serotonin release assay (SRA) that has a sensitivity of greater than 95% and a specificity of approximately 90% for the detection of platelet activating antibodies.²³ If HIT is suspected and/or confirmed, UFH will be discontinued for the duration of the study period, and an alternate non-heparin-based anticoagulant will be instituted at the discretion of the investigator. Subsequently, the SRA will be performed to confirm or exclude the diagnosis. The SRA will be collected by the inpatient phlebotomy team or nursing staff and sent to the inpatient laboratory for analysis. A known history of HIT will result in exclusion from study participation.

Risk of inadvertent disclosure

Study participation and related data will be protected to maintain confidentiality. There is a possibility that the subject's personal information could become generally known. This information could impact future insurability, employability, have a negative impact on family relationships, or result in stigmatization. In order to reduce risks of disclosure or breach of confidentiality, the research related documents, blood samples, and clinical information stored in the subject's research file will be assigned an alphanumeric identifier, i.e. ACS001, which does not contain any personal identifying information. A linkage key for linking the assigned alphanumeric identifier with the subject's name will be stored in locked files at HCWP. Any publication arising from this study will not contain names or other identifying information.

Potential benefits

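### Thrombocytopenia is counted as any platelet count below 100,000 with no reference to baseline, although patients entering at 50,000 to 99,999 are eligible and a large fall that stays at or above 100,000 is recorded only by judgement

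*Combined protocol and SAP*

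**What the plan says.** Section 4.4 (Risk/Benefit Ratio, item 3) gives the event definition: "Thrombocytopenia will be defined as a platelet count less than 100,000 per microliter". It contains no requirement for new onset and no fall from baseline. The same item sets the entry floor: "A baseline platelet count less than 50,000 per microliter will result in exclusion from study participation". Exclusion criterion 2 in Section 4.3 prints a different floor: "Platelet count less than 50 per microliter (current admission".

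Section 3.3 names thrombocytopenia among the heparin risks: "Potential adverse events include heparin-associated risks, such as allergic reaction, major bleeding, minor bleeding, thrombocytopenia". The sentence goes on to list HIT separately and adds an open category: "thrombocytopenia, and heparin induced thrombocytopenia (HIT), or any other adverse reaction suspected secondary to drug administration". The safety evaluation is limited to subjects who received any UFH, and adverse events are to be tabulated by how often they occur, how severe they are and how they relate to treatment. Platelets are required daily from randomization to study completion in UFH subjects.

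For HIT, Section 4.4 (item 4) says that "the diagnosis requires a compatible clinical picture and laboratory evidence of platelet activating antibodies", without stating what platelet change should raise suspicion. Section 4.6 records all adverse events, allows an abnormal laboratory result to be one, and requires each to be graded for causality.

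**The concern.** The event threshold lies above the entry floor, so the definition cannot separate a low count that the patient brought into the trial from one that appeared on heparin. In the other direction, the size of a fall plays no part: a trivial change across 100,000 is an event, while a much larger change that ends above it is not.

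At stake is the thrombocytopenia line in the safety summary, which a phase III trial may use for planning and whose definition it may inherit. No control-arm frequency is planned, so each patient's own baseline is the main means of separating a pre-existing state from a drug effect. Elsewhere the protocol does refer to the patient's starting point: major bleeding includes a hemoglobin decrease of 2 grams per deciliter, and hypoxemia is redefined for patients with an abnormal baseline saturation or oxygen need. The platelet definition has no such term.

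**Working it through.** The plan gives no figure to reproduce: the sample size of 20 is stated to be non-statistical and no platelet distribution is given. The check compares the rules and then shows what they imply.

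**Inputs.** Event: count below 100,000 (4.4). Entry floor: 50,000 (4.4), or 50 as printed (4.3). UFH arm: 10 patients (4.2, 1:1 allocation of 20). Background risk of non-immune thrombocytopenia: 5 to 30% (4.4).

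**1. Overlap.** Under Section 4.4, baselines from 50,000 to 99,999 are eligible and already below 100,000. Such a patient meets the definition with 0% change. The floor in Section 4.3, read literally, is lower by a factor of 50,000 / 50 = 1,000, which on its own would widen the overlap.

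**2. Small change, event.** A fall from 101,000 to 99,000 is 2,000 / 101,000 = 2.0% and is an event.

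**3. Large change, no event under this definition.** A fall from 400,000 to 110,000 is (400,000 − 110,000) / 400,000 = 72.5%. The largest fall that does not meet the definition ends at exactly 100,000 and equals 1 − 100,000 / baseline:

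| Baseline | Largest fall not meeting the definition |
|---|---|
| 200,000 | 50.0% |
| 300,000 | 66.7% |
| 400,000 | 75.0% |
| 500,000 | 80.0% |

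**4. Weight of one patient.** 1 / 10 = 10 percentage points.

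**5. Sensitivity.** Let q be the share of patients entering at 50,000 to 99,999. The documents give no value, so the q below are assumptions. Let p be the risk of a true new event in the remaining patients, set to the two ends of the background range purely for illustration. Assume that patients are independent and that every patient who enters low has at least one count below 100,000 after UFH starts. Then:

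- chance of at least one pre-existing case among 10 = 1 − (1 − q)^10
- apparent rate = q + (1 − q)p
- pre-existing share of events = q / apparent rate

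| q (assumed) | At least one of 10 | Apparent rate, p = 5% | Pre-existing share | Apparent rate, p = 30% | Pre-existing share |
|---|---|---|---|---|---|
| 2% | 18% | 6.9% | 29% | 31.4% | 6% |
| 5% | 40% | 9.75% | 51% | 33.5% | 15% |
| 10% | 65% | 14.5% | 69% | 37.0% | 27% |
| 20% | 89% | 24.0% | 83% | 44.0% | 45% |

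For example, with q = 5% and p = 5%: 0.05 + 0.95 × 0.05 = 0.0975, and 0.05 / 0.0975 = 51%.

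**The case against.** A reader might infer that a steep fall from a high count is never an event. The documents do not support that. Any fall ending below 100,000 is an event, however high the start. One that stays at or above 100,000 misses only the named definition and can still be recorded as suspected HIT, under the open category in Section 3.3, or as an abnormal laboratory finding under Section 4.6. What stands is that these routes depend on judgement: none states a platelet change that triggers them.

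A reader might also infer that every low entry count would be reported as heparin harm. That is not established either. Section 4.6 defines an adverse event in a subject to whom a product is administered, so a count before UFH is not formally one. Each event is graded for causality, the possibly-related grade allows for concurrent disease, and abnormal values are followed until they return to baseline. The difficulty begins with the first unchanged count after UFH starts. The not-related grade requires both an explanation other than UFH and the absence of a temporal relationship, and a low count during infusion fits the second condition poorly.

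Third, a reader might set the observed rate against Section 4.4's statement that "The risk of non-immune related thrombocytopenia with heparin varies anywhere between 5 and 30" percent. The plan gives that range as background and schedules no such comparison.

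Finally, no stated decision rests on this event. Thrombocytopenia is not a safety-committee review event in Section 4.5, a feasibility criterion or a clinical outcome, and all comparisons are descriptive. This limits the consequence to the accuracy of a reported safety frequency; it does not make the definition sound.

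**Conclusion.** The point holds in a limited form. As written, the definition can count an unchanged pre-existing low count in the UFH thrombocytopenia frequency, and it leaves large falls that stay at or above 100,000 to judgement. Each patient so misclassified moves the frequency by 10 points if all 10 allocated patients receive UFH. How often this would happen is unknown, because it depends on a baseline platelet distribution that the documents do not give; the sensitivity table shows a range under assumed shares and is not a prediction. The conclusion takes the 50,000 entry floor in Section 4.4 as operative and rests on the absence of any new-onset or change-from-baseline rule anywhere in the document.

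**What to change.** For safety reporting, add to Sections 4.4 and 3.3:

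- Record the last platelet count before UFH starts as the baseline.
- Count thrombocytopenia as new onset only when that baseline was 100,000 or more and a later count is below 100,000.
- List patients with a baseline below 100,000 separately, with their counts.
- Report each UFH patient's nadir as a percentage of baseline.

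Reconcile the platelet entry floors in Sections 4.3 and 4.4, since they determine which patients fall in the overlap.

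The cost is one derived variable and one or two more lines in the safety table. No extra sampling is needed: eligibility already calls for a platelet count from the current admission, and daily counts follow in UFH subjects. The change concerns only how events are counted and displayed. The rules for stopping and resuming UFH are not addressed here.

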4. HIT

HIT is an immunologically mediated thrombotic state that occurs in 1-2% of patients receiving heparin therapy.²³ Antibodies of the IgG class recognize large macromolecular complexes of platelet factor 4 bound to heparin.²³ Subsequently, these antibodies produce strong activation of platelets by binding to platelet Fc γ IIa receptors.²³ The ensuing thrombotic state may lead to arterial and venous thrombosis, skin necrosis, venous limb gangrene, stroke, and myocardial infarction. The diagnosis of HIT is a clinical-pathologic syndrome, which means the diagnosis requires a compatible clinical picture and laboratory evidence of platelet activating antibodies.²³ The laboratory diagnosis of HIT will be made with the serotonin release assay (SRA) that has a sensitivity of greater than 95% and a specificity of approximately 90% for the detection of platelet activating antibodies.²³ If HIT is suspected and/or confirmed, UFH will be discontinued for the duration of the study period, and an alternate non-heparin-based anticoagulant will be instituted at the discretion of the investigator. Subsequently, the SRA will be performed to confirm or exclude the diagnosis. The SRA will be collected by the inpatient phlebotomy team or nursing staff and sent to the inpatient laboratory for analysis. A known history of HIT will result in exclusion from study participation.

Risk of inadvertent disclosure

Study participation and related data will be protected to maintain confidentiality. There is a possibility that the subject's personal information could become generally known. This information could impact future insurability, employability, have a negative impact on family relationships, or result in stigmatization. In order to reduce risks of disclosure or breach of confidentiality, the research related documents, blood samples, and clinical information stored in the subject's research file will be assigned an alphanumeric identifier, i.e. ACS001, which does not contain any personal identifying information. A linkage key for linking the assigned alphanumeric identifier with the subject's name will be stored in locked files at HCWP. Any publication arising from this study will not contain names or other identifying information.

Potential benefits

UFH may result in a decrease in the duration of hospitalization, hypoxemia, fever, leukocytosis, moderate to severe pain, and the number of red blood cell transfusions administered; however, as this is a pilot study, specifically designed to evaluate predefined feasibility criteria for conducting a large scale clinical trial, there may be no benefit from participation in the study.

4.5 Data Safety Monitoring Plan (DSMP)

The Data Safety Monitoring Committee (DSMC) will meet at least weekly to review all aspects of the study. The DSMC is comprised of the research team at HCWP consisting of three physicians ([name], [name], and another hematologist), two research nurses, and one regulatory coordinator. Subjects will be closely monitored to ensure subject safety and to ensure that procedures are in place to maintain privacy and confidentiality, progress of study, integrity of the data, procedure reviews, and for discussion of pertinent scientific literature or events which could effect the benefit to risk ratio. All serious and unexpected adverse events and/or major breaches of confidentiality will be reported to the IRB according to regulations outlined in the IRB *Reference Manual for the Use of Human Subjects*. The DSMC will determine if the risk benefit ratio is sufficiently favorable that it is appropriate to continue the trial. The events are:

- A subject develops major bleeding in association with UFH.
- A subject develops HIT in association with UFH.
- A subject develops a Grade 2 or greater allergic reaction in association with UFH, defined as follows using the CTCAE grading.
 - Grade 2 - Intervention or interruption of infusion necessary. Responds promptly to symptomatic treatment. Prophylactic medications indicated for less than or equal to 24 hours.
 - Grade 3 - Prolonged, or not rapidly responsive to symptomatic treatment and/or interruption of infusion. Recurrence of symptoms following initial improvement.
 - Grade 4 - Life-threatening consequences. Urgent intervention indicated.
- A subject develops anaphylaxis in association with UFH, defined as follows using the CTCAE grading (all anaphylactic events are Grade 3 or higher).
 - Grade 3 - Symptomatic bronchospasm with or without urticaria. Allergy-related edema and/or angioedema. Hypotension. Parenteral intervention needed.
 - Grade 4 - Life-threatening consequences. Urgent intervention indicated.

Such events will be handled as serious adverse events (SAEs) and reported in an expedited time frame to the IRB. The data concerning the event will be reviewed by the DSMC along with all other available data to determine appropriate follow-up, with a decision to continue enrollment and treatment of subjects at that time. Additionally, the following may also stop further subject enrollment and treatment.

- The DSMC warrants temporary suspension of enrollment for further review of data generated to date.
- The investigator determines that a medically important event warrants further evaluation by the DSMC.

A report summarizing the above DSMP activities will be submitted to the IRB at the time of annual renewal.

4.6 Adverse Event Reporting

All adverse events (AE) experienced by study subjects are to be recorded on the CRF, regardless of the severity of the event or its relationship to study treatment. The AE reporting procedures are based on the CTCAE system, volume 4.03, 2010. Subjects will report any symptoms to the investigator, research staff, inpatient nursing staff, or treating physician. [name] will determine if symptoms qualify as an AE or SAE with confirmation by [name]. AEs will be classified as mild (does not interfere with routine activities), moderate (interferes somewhat with routine activities), or severe (impossible to perform routine activities). The following algorithm will be used to assess the causality of all AEs:

- **Not related:** The event can readily be explained by factors not involving UFH, and a temporal relationship with UFH does not exist.
- **Possibly related:** A clinical event, including laboratory test abnormality, with a reasonable time sequence to administration of UFH but which could also be explained by concurrent disease or other drugs or chemicals. Information on drug withdrawal may be lacking or unclear.
- **Probably related:** The temporal relationship between the administration of UFH is compelling, and the event cannot be explained by the subject's medical condition or other therapies.
- **Related:** The event follows a reasonable temporal sequence from the administration of UFH, follows a known or suspected response pattern to UFH, is confirmed by improvement upon stopping UFH, and reappears upon repeated exposure to UFH.

The investigator will follow up all AEs, regardless of severity, until satisfactory resolution. All subjects experiencing AEs will be monitored until symptoms subside and any abnormal laboratory values have returned to baseline, or until there is a satisfactory explanation for the changes observed, or until death, in which case a full pathologist's report will be supplied, if possible. Withdrawal from the clinical study and therapeutic measures shall be at the discretion of the investigator. As required by the IRB, if there is a serious, unexpected or adverse event that is determined to be associated with UFH, it will be reported to the IRB within 24 hours. If the event is not serious, unexpected or related to UFH, it will be reported within 5 days. All events must be assessed to determine the following:

- If the event meets the criteria for an SAE.
- The relationship of the event to study treatment.
- The severity of the event.

An AE is any untoward medical occurrence in a subject in whom a pharmaceutical product is administered but does not necessarily have a causal relationship with the pharmaceutical product. An AE can therefore be any unfavorable and unintended sign (including an abnormal laboratory finding), symptom, or disease temporally associated with the use of a pharmaceutical product, whether or not related to the pharmaceutical product.²⁷ A SAE is any untoward medical occurrence that at any dose:

- Results in death.
- In the view of the investigator, places the subject at immediate risk of death.
- Requires inpatient hospitalization or prolongation of existing hospitalization.
- Results in persistent or significant disability/incapacity.
- Results in a congenital anomaly/birth defect.

An SAE may also be any other medically important event that, in the opinion of the investigator, may jeopardize the subject or may require intervention to prevent one of the other outcomes listed in the definition above.

